within 30 days; (3) MDD symptoms, as measured by the PHQ-9²); and (4) PTSD symptoms, as measured by the PCL-5.¹⁷⁹ MOUD continuity and access will be based on prescription (data and frequency) data from the EHR, supplemented by New Mexico Prescription Drug Monitoring Program data if feasible.

During data collection and prior to breaking the study blind, we changed the operationalization of the first two primary outcomes due to data quality issues. Both outcomes were revised to focus on buprenorphine rather than MOUD, due to missing methadone data. Under federal regulations, primary care providers are not permitted to initiate or prescribe methadone for OUD and there is no objective data on methadone initiation from methadone treatment programs equivalent to the data in the PMP. We also do not include injectable naltrexone because in our data fewer than 1% reported receiving it.

We also changed the specification of MOUD continuity of care to be operationalized as cumulative days of care, removing the requirement for no breaks in care of more than seven days. It is important to note that there is no “gold standard” for measuring OUD quality of care.²¹⁰⁻²¹² While the National Quality Forum measure on which our measure is based has a requirement for no breaks in care, we believe that this requirement introduces measurement bias. We know from clinical experience and the scientific literature, medication nonadherence is common, and that patients will reduce their dose due to cost barriers or in an attempt to wean themselves off, introducing measurement bias.^{213,214} Measures of buprenorphine adherence do not include the requirement for no breaks in care^{215,216} and patients with percent days covered of >0.80 are classified as adherent. While it is widely agreed upon that longer MOUD care is better, there is no empirical evidence of an ideal length of time, or for how breaks in care are related to long-term outcomes such as mortality.^{48,217,218} Recent studies have cautioned against rigidly defining MOUD success and continuity due to patients’ nonlinear treatment trajectories and the crucial impact of MOUD even after gaps in care.^{211,219,220} Therefore, we believe it is both more meaningful and more valid to assess OUD quality of care as a count of total days of MOUD treatment rather than rely on a contested definition of care discontinuity.

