9.3 POPULATIONS FOR ANALYSES

All analyses are intention-to-treat based on randomization. The primary study outcomes have the following analysis populations:

1. Buprenorphine access is limited to randomized participants with a new OUD episode of care at enrollment, defined as no visits with an OUD diagnosis in the past 30 days.
2. Cumulative days of buprenorphine for OUD includes all randomized participants.
3. Depression symptom severity includes all randomized participants with likely depression at enrollment, defined as PHQ-8³ ≥ 10 .
4. PTSD symptom severity includes all randomized participants with likely PTSD at enrollment, defined as PC-PTSD-5³ ≥ 3 .

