2.5 Definitions of outcomes

2.5.1 Primary outcomes

Table 1 defines the primary outcomes of this study. The hypotheses associated with these outcomes are as follows:

1. We hypothesize that patients with a new OUD episode of care who are randomized to CC-COD/CC-COD+ will receive buprenorphine within fewer days after that care episode

than new OUD patients who are randomized to enhanced usual care. Alternatively, the null hypothesis is that there will be no difference in the number of days until receipt of buprenorphine with a new OUD episode of care.

2. We hypothesize that patients who are randomized to CC-COD/CC-COD+ will have more days of buprenorphine treatment within 180 days of study enrollment than patients who are randomized to enhanced usual care. Alternatively, the null hypothesis is that there will be no difference in the number of days of cumulative buprenorphine treatment within 180 days of study enrollment.
3. We hypothesize that, among patients with probable depression at study enrollment, those who are randomized to CC-COD/CC-COD+ will have a greater reduction in depression symptoms 6 months after study enrollment compared to those who are randomized to enhanced usual care. Alternatively, the null hypothesis is that there will be no difference in depression symptoms 6 months after study enrollment among those with probable depression at enrollment.
4. We hypothesize that, among patients with probable PTSD at study enrollment, those who are randomized to CC-COD/CC-COD+ will have a greater reduction in PTSD symptoms 6 months after study enrollment compared to those who are randomized to enhanced usual care. Alternatively, the null hypothesis is that there will be no difference in PTSD symptoms 6 months after study enrollment among those with probable PTSD at enrollment.

A union-intersection test will be used to test the overall success of the study that combines the four primary outcomes into a single composite hypothesis. In particular, the null hypothesis is the intersection of the four primary outcome null hypotheses (i.e., all null hypotheses are true), and the alternative is the union of the alternative hypotheses (i.e., at least one alternative hypothesis is true). As described in subsequent sections, either a Bonferroni or Benjamini-Hochberg correction on the individual hypotheses will be used to control the error rate of this composite test.

Table 1: Definition of primary outcomes

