Outcome	Population ^a	Definition	Measure Scale	Source
Buprenorphine access	Study participants with a new episode of OUD care (no care for at least 30 days prior)	Number of days until first buprenorphine prescription after study enrollment	Time-to-event	Survey, PMP
Buprenorphine continuity of care	Study participants not on methadone at baseline	The cumulative number of days the patient receives buprenorphine during the 180 days after study enrollment.	Continuous	Survey, PMP
MDD symptom severity	Study participants with probable MDD at baseline (PHQ-8 \geq 10)	PHQ-9 at 6 months	Sum of items (0-27)	Survey
PTSD symptom severity	Study participants with probable PTSD at baseline (PC-PTSD-5 \geq 3)	PCL-5 at 6 months	Sum of items (0-80)	Survey

^a Study participants means all study participants who consented and were randomized to the intervention or to EUC.

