3.5.1 Primary outcomes

We used the observed distributions for our continuous variables including the following: for the planned power calculations were:

1. We observed a mean number of days until accessing Buprenorphine of 26.0 with a standard deviation of 31.9. Our total sample size for this analysis was 137 individuals with 6-month follow-up data.
2. Among those who initiate medication for OUD, the mean number of days of continuous treatment for OUD is 133.0 with a standard deviation is 54.1. The total sample size for this analysis was 392 individuals with 6-month follow-up data.
3. Among those with probable depression at enrollment ($\text{PHQ-8} \geq 10$), the mean depression symptoms score (PHQ-8) at 6 months of 11.5 with a standard deviation of 6.6. The total sample size for this analysis was 405 individuals with 6-month follow-up data.
4. Among those with probable PTSD at enrollment ($\text{PC-PTSD-5} \geq 3$), the mean PTSD symptoms score (PCL-5) at 6 months of 32.2 with a standard deviation of 17.8. The total sample size for this analysis was 368 individuals with 6-month follow-up data.

Under these observed outcome distributions as well as the final number of individuals with observed outcome values in our data, we have 80% power to detect:

1. A hazard ratio of at least 0.45 if we find a protective effect and see fewer days until accessing Buprenorphine. This corresponds to at least a hazard ratio of 2.25 if the direction were reversed or a 27-percentage point difference if the outcome was modeled as a binary measure. Notably, a previous study of Collaborative Care for opioid and alcohol use disorders found a 22-percentage point increase over enhanced usual care so if the effect is large in CLARO, we may be able to detect it.⁸
2. 18.3 additional days of continuous OUD treatment within the first 180 days. A growing body of evidence suggests the mortality is lower during OUD treatment, and that mortality is increased in the first four weeks after treatment cessation.⁹
3. A 2.2 point reduction in depression symptoms (PHQ-8). This provides power to detect effects below the clinically important difference for individual change of 5 points.¹⁰
4. A 6.23 point reduction in PTSD symptoms (PCL-5). A previous study of delivering PTSD treatment in primary care setting to active duty military found a reduction in PTSD symptoms of 7 points.¹¹

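### SAP 3.5.1 states the detectable effect for buprenorphine continuity in continuous days among initiators, but the endpoint is cumulative days, no analysis uses that group, and the documents name conflicting populations

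*SAP*

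**What the plan says.** SAP 3.5.1 presents its inputs as observed distributions. For continuity of care it reads "Among those who initiate medication for OUD, the mean number of days of continuous treatment for OUD is 133.0", with SD 54.1, and adds "The total sample size for this analysis was 392 individuals with 6-month follow-up data". The detectable effect at 80% power and a 1.25% Type I error rate is "18.3 additional days of continuous OUD treatment within the first 180 days".

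The endpoint is defined differently elsewhere. SAP Table 1 gives "The cumulative number of days the patient receives buprenorphine during the 180 days after study enrollment", and protocol sections 3, 8.1 and 9.1 agree. Protocol 8.1 records the change explicitly: "We also changed the specification of MOUD continuity of care to be operationalized as cumulative days of care". It drops the no-breaks rule and narrows the medication to buprenorphine.

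The analysis population is described as follows:

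- Protocol 9.3: "Cumulative days of buprenorphine for OUD includes all randomized participants".
- SAP 3.4.2: primary analyses use the intention-to-treat population of all randomised subjects.
- SAP Table 1: "Study participants not on methadone at baseline".
- SAP hypothesis 2: "We hypothesize that patients who are randomized to CC-COD/CC-COD+ will have more days of buprenorphine treatment within 180 days of study enrollment", with no restriction, although hypotheses 1, 3 and 4 each name their subgroup.
- SAP 3.5.1: those who initiate medication for OUD.

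**The concern.** There are two separate problems.

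The first is the power statement. It attaches a mean, SD and N to a set of people that no analysis section uses, and to an endpoint (continuous treatment with OUD medication) that was replaced by cumulative buprenorphine days. Starting medication happens after randomisation, and hypothesis 1 expects the intervention to speed it up, so a comparison among starters would not be a randomised one. Under the Table 1 definition, someone who never starts contributes 0 days. Including such people changes both the mean and the SD.

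The second is the population itself. Whether participants on methadone at baseline are in or out is answered differently in different places. For one of four primary endpoints, each tested at 1.25%, that should be fixed in advance. Otherwise the choice can later look as if it was made from the data.

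The calculation was made after data collection, so no recruitment decision depends on it. It will, however, shape how a null result on this endpoint is read.

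**Working it through.** **Inputs.** Two-sided tests (SAP 3.4.2), alpha 0.0125 and power 80% (SAP 3.5), 1:1 allocation (SAP 2.7), mean 133.0, SD 54.1 and N=392 (SAP 3.5.1), 797 enrolled (SAP 2.6).

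**Reproducing 18.3.** For two equal arms, detectable difference = (z for 1 − 0.0125/2 + z for 0.80) × SD × 2/√N = (2.498 + 0.842) × 54.1 × 2/√392 = 18.25 days. With the noncentral t distribution it is 18.32, matching the SAP. The same unadjusted t calculation gives 2.20 for PHQ (SD 6.6, N=405; SAP 2.2) and 6.22 for PCL-5 (SD 17.8, N=368; SAP 6.23). The SAP figures therefore appear to be unadjusted, and unadjusted scenarios are a like-for-like comparison.

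**Adding people with 0 days.** If a share p start, with mean 133.0 and SD 54.1, and the rest have 0 days, the SD over everyone is √(p × 54.1² + p(1 − p) × 133.0²). The documents give neither the SD nor the N for either named population, so three readings are possible.

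*Reading 1: only the label is out of date.* If 133.0 and 54.1 already describe the planned set, 18.3 stands. This can be tested. The share with a non-zero value must be at least 133.0²/(133.0² + 54.1²) = 17,689/20,615.8 = 85.8%. At most 14.2%, or 55 of the 392, can then have 0 days.

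*Reading 2: the 392 are starters and everyone else analysed has 0 days* (p = 392/N, total N assumed):

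| Total N | p | SD | Detectable days | Power at 18.3 |
|---|---|---|---|---|
| 420 | 0.933 | 61.9 | 20.25 | 70% |
| 504 | 0.778 | 73.0 | 21.79 | 62% |
| 525 | 0.747 | 74.4 | 21.74 | 62% |
| 600 | 0.653 | 76.9 | 21.03 | 66% |
| 700 | 0.560 | 77.4 | 19.59 | 73% |
| 797 | 0.492 | 76.6 | 18.15 | 81% |

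525 is the largest follow-up N in SAP Table 9. 797 is everyone enrolled, the population protocol 9.3 names. At that N the stated figure is about right.

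*Reading 3: the 392 are the whole set, and 133.0 and 54.1 describe only the starters among them.* At 95% starters the SD is 60.2 and the detectable effect 20.38 days (69% power at 18.3). At 80% they are 71.9 and 24.36 days (50% power, 0.505). Nothing in the documents supports a particular share.

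**Covariates.** SAP 3.4.4 adjusts for health system and prior MOUD, which could lower these figures. The share of variance needed to return to 18.32 is 1 − (18.32/detectable effect)²: 18% at N=420 and 29% at N=504 under reading 2; 19% at 95% starters and 43% at 80% under reading 3.

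**The case against.** The strongest reply is that this is stale wording and nothing more. The sentence closely follows assumption 4 in protocol 9.2, where continuous days among initiators were the original planning basis. The SAP revision table says the power calculations were redone for the modified outcomes, and SAP 3.5.1 says it used the final number of people with observed outcome values. Labels in that section are loose elsewhere: item 3 refers to the PHQ-8 at 6 months, where Table 1 has the PHQ-9. All of this supports reading 1, though it does not prove it, and the text would still need correcting.

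On the population, the protocol defers to the SAP for detail, and SAP 2.5.1 says that Table 1 defines the primary outcomes. A reader who follows that chain reaches participants not on methadone at baseline. That is a fair default. It does not remove the conflict with the intention-to-treat sentence in SAP 3.4.2 or with protocol 9.3.

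On consequence, no test, alpha level or sample size depends on 18.3, and a null result can be read from the confidence interval. That stands, and it limits the weight of the power component.

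A reader might go further and infer that the endpoint is underpowered, or that the sponsor intends to analyse initiators only. The documents support neither. Power at 18.3 days is 81% if the 392 are starters among all 797, and every analysis section that names a population for this endpoint names one defined at or before randomisation.

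**Conclusion.** The point holds as a contradiction in the documents, not as a demonstrated loss of power. SAP 3.5.1 describes the wrong endpoint and a group that no analysis uses, and the population for a primary endpoint differs between protocol 9.3 and SAP 3.4.2 on one side and SAP Table 1 on the other. Confidence in that is high.

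The size of any error in 18.3 cannot be fixed from the text. It is nil under reading 1. Under reading 2 the detectable effect is about 20 to 22 days for N of 420 to 600, falling to 19.6 at 700 and about 18.1 at 797. Under reading 3 it is about 20 to 24 days at 95% to 80% starters. So 18.3 may be optimistic or about right. These are scenarios, not bounds. They are unadjusted, and readings 2 and 3 assume that 133.0 and 54.1 apply to starters and that all others have exactly 0 days. The matter should be fixed, with the population conflict the more important part.

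**What to change.** Choose one population for continuity, defined at baseline, and state it identically in protocol 9.3, SAP 3.4.2, SAP hypothesis 2 and SAP Table 1. Say explicitly that participants who never start buprenorphine count as 0 days.

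In SAP 3.5.1, replace the references to continuous treatment and to those who initiate medication. Confirm who the 392 are and how many of them have 0 days; more than 55 would rule out reading 1. Then restate the mean, SD, N and detectable effect for cumulative buprenorphine days in the chosen population, using data pooled across arms.

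The cost is wording changes in both documents and one recalculation. The stated detectable effect may become somewhat less favourable.

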2.2 Blinding

The research staff will be blind to the treatment assignment and participant outcomes until database lock, except for research assistants at the point of randomization. All aspects of this analysis plan were finalized prior to unblinding. Clinic staff and participants will not be blind to the treatment assignment, as it is not possible to deliver the intervention with blinding.

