2.6 Study design

This study is a stratified randomized trial testing CC-COD versus EUC, with strata defined by prior MOUD exposure and primary care clinic.

As part of the CR, we initially planned to compare CC-COD+ to CC-COD, with MOUD continuity of care as the primary outcome. However, despite sustained and targeted efforts, recruitment was lower than expected, and we did not reach our targeted enrollment goals for either CC-COD or CC-COD+. Based on input from our research advisory board and NIH project officer, we now plan to combine the CC-COD and CC-COD+ samples when analyzing the data for additional information about the potential effectiveness of the intervention. Since the Collaborative Care Model is identical across both trials, and the only difference between the arms is in the additional clinical modules supported by CC-COD+, combining the active CC-COD and CC-COD+ arms for an exploratory analysis should provide additional precision around the estimated treatment effect for CC-COD/CC-COD+.

The study's original target sample size was 900, with an additional 300 patients targeted for the CR, for a combined target of 1200. Our final sample size was 797 (729 following the original protocol and 68 following the protocol from the CR). This analysis plan has been modified to include actual final power calculations calculated prior to breaking the blind but after all data collection ended.

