3.4.5 Survival outcome

Buprenorphine access, the survival outcome that is measured in the PMP and survey will be analyzed using a Cox proportional hazard regression model including health-system, prior MOUD exposure, and treatment assignment as predictors. The Cox proportional regression model is given by:

$$h(t) = h_0(t) * \exp(\alpha_j + \nu P_{ij} + \beta T_{ij})$$

where α_j are health system-level fixed effects, and e^β is the hazard ratio effect of CC-COD over EUC. The statistical hypotheses from the Cox proportional hazard regression will be of the form:

$$H_0: \beta = 0 \text{ vs}$$
$$H_1: \beta \neq 0.$$

Outcomes that are measured as part of the 6-month follow-up survey may be weighted to account for nonresponse as previously described. Again, if we do not have sufficient sample size to support modeling P_{ij} (prior MOUD treatment), then it will be removed from a given model. We will assess this for each continuous outcome by examining if we have at least 30 individuals with and without prior MOUD treatment in our analytic sample. We will right censor all observations for those individuals who did not ever receive buprenorphine during the course of follow-up for these analyses.

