3.5.2 Secondary outcomes

Secondary endpoints are grouped into domains of conceptually related endpoints, and the outcomes will be analyzed adjusting for multiple comparison within domain using a Bonferroni correction. Table 8 provides the grouping of the secondary outcomes into domains, along with the observed outcome distributions, the minimum detectable effect size at 80% power and a family-wise error rate of 5%, and a reference effect size (if available). The vast majority of secondary outcomes are sufficiently powered to detect clinically meaningful effects or effects found in similar interventions.

Table 9: Minimum detectable effect size for secondary outcomes

Outcome	Observed distributions	Minimum detectable effect size	Reference effect size
Mental Health			
Access to MDD and/or PTSD treatment	
 • N=259 • 65.5% access treatment 	19.2 percentage points	None
Quality of care for MDD	
 • N=210 • 8.8% with quality care 	18.9 percentage point	16 percentage points for medication adherence ¹² at 3 months
Quality of care for PTSD	
 • N=300 • 9% with quality care 	15.3 percentage point	Expect similar to MDD
MDD remission	
 • N=405 • 16.0% remission 	15.0 percentage points	15 percentage points ¹³
MDD response	
 • N=405 • 26.2% response 	15.8 percentage points	20 percentage points from CALM ¹³ or 23 percentage points from STEPS-UP ¹¹
PTSD remission	
 • N=368 • 56.2% remission 	17.8 percentage points	Similar to MDD remission
PTSD response	
 • N=365 • 21.6% response 	17.7 percentage points	18 percentage points ¹¹

Active suicidal ideation	
• N=523• 24.2% at 6-months	14.5 percentage point	Any reduction
--------------------------	---	-----------------------	---------------

Substance Use

Opioid use frequency	
• N=523• Mean (sd) = 4.3 (9.6)	0.27 standard deviations; 2.6 raw scale	None
----------------------	---	---	------

Opioid overdose events	
• N=525• 2.1% at 6-months	5.9 pct point reduction	None
------------------------	--	-------------------------	------

Overall Health

Physical health functioning	
• N=525• Mean (sd) = 36.8 (12.0)	3.2 points	Similar to mental health functioning

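### SAP power text labels HR 0.45 as faster buprenorphine access, prints an impossible overdose reduction, and claims more power for secondary outcomes than Table 9 shows

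*SAP*

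**What the plan says.** Hypothesis 1 in SAP 2.5.1 is that CC-COD/CC-COD+ patients "will receive buprenorphine within fewer days after that care episode" than EUC patients. SAP 3.4.5 fits a Cox model in which the exponentiated treatment coefficient "is the hazard ratio effect of CC-COD over EUC", and right-censors people who never receive buprenorphine.

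SAP 3.5.1 then states the detectable effect for N=137 as "A hazard ratio of at least 0.45 if we find a protective effect and see fewer days until accessing Buprenorphine". The next sentence gives "a hazard ratio of 2.25 if the direction were reversed or a 27-percentage point difference" on a binary scale, and adds that a previous collaborative care study "found a 22-percentage point increase over enhanced usual care so if the effect is large in CLARO, we may be able to detect it". No event count is given.

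Table 9 in SAP 3.5.2 lists overdose events at N=525 and 2.1%, with a minimum detectable effect of "5.9 pct point reduction". Active suicidal ideation is at N=523 and 24.2%, with a detectable effect of 14.5 points, and its reference is any reduction. The text above the table says that nearly all secondary outcomes have adequate power for clinically meaningful effects or for effects seen with similar interventions. The SAP makes the same claim for every exploratory outcome, and Protocol 9.2 makes it for the secondary outcomes.

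On timing, SAP 2.6 describes "actual final power calculations calculated prior to breaking the blind but after all data collection ended", and SAP 2.2 says "All aspects of this analysis plan were finalized prior to unblinding".

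**The concern.** Three statements do not agree with the SAP's own definitions or figures. When the event is receipt of treatment, a ratio of 0.45 for CC-COD over EUC means slower access, which is the opposite of the label attached to it. An outcome at 2.1% cannot fall by 5.9 points. The summary on secondary power also sits above a table whose reference column, the only benchmark the SAP gives for these outcomes, is missed about as often as it is met.

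A reader facing a null result will turn to this section to ask what the trial could have missed. One primary endpoint has its benefit direction mislabelled. Overdose, a safety-relevant secondary endpoint with about 11 events (0.021 × 525 = 11.0), is credited with a detectable benefit that cannot exist.

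**Working it through.** **Inputs.** Two-sided tests (SAP 3.4.2), 1:1 allocation (SAP 2.7) and 80% power. Alpha is 0.05/4 = 0.0125 for primary outcomes. Bonferroni within domain gives 0.05/8 = 0.00625 for mental health, and 0.05/2 = 0.025 for substance use and for overall health. N, rates and SDs are from SAP 3.5.1 and Table 9.

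**Hazard ratio.** The reciprocal is 1/0.45 = 2.22 (printed as 2.25). Schoenfeld events = 4(z₁₋α/₂ + z₀.₈)²/(ln HR)² = 4(2.498 + 0.842)²/(ln HR)². This gives 70 events for 0.45 and 68 for 2.25; Freedman's formula gives 78 and 76. The magnitude therefore fits roughly half of the 137 having the event (70/137 = 51%). That fraction is inferred, because no count is stated.

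**Overdose.** Power = Φ{[|p₁−p₂|√n − z√(2p̄(1−p̄))] / √(p₁(1−p₁)+p₂(1−p₂))}, with n = 262.5 per arm and z = 2.241. Taking 2.1% to 8.0%: [0.059×16.20 − 2.241×0.3097]/0.3069 = 0.853, so power is 80.3%. The 5.9 reproduces as an increase. As a fall it is impossible: the limit is 2.1 points if 2.1% is the EUC rate, or 4.2 (4.2% v 0%) if it is pooled.

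Exact power for complete elimination (2.1% v 0%, 262 per arm, alpha 0.025) depends on the test. Against zero events in the other arm:
- Fisher rejects from 7 events: power 0.31 (0.47 if EUC has 262 and the other arm 263)
- pooled z-test rejects from 5 events: 0.65
- likelihood-ratio test of an unadjusted two-arm logistic model rejects from 4 events (LR 5.58 > 5.02): 0.80, with type I error about 0.030 at 2.1% in both arms

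For a halving (2.1% v 1.05%), the three give 0.05, 0.09 and 0.12.

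**Binary rows of Table 9.** Detectable difference in points, same formula:

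| Outcome | Printed | Increase, observed rate as EUC rate | Observed rate pooled | Reference |
|---|---|---|---|---|
| Access to MDD/PTSD treatment | 19.2 | 19.1 | 21.0 | none |
| MDD quality | 18.9 | 18.9 | 13.9 | 16 |
| PTSD quality | 15.3 | 15.3 | 11.8 | about 16, by analogy |
| MDD remission | 15.0 | 15.0 | 13.0 | 15 |
| MDD response | 15.8 | 16.9 | 15.6 | 20 (or 23) |
| PTSD remission | 17.8 | 17.7 | 18.4 | about 15, by analogy |
| PTSD response | 17.7 | 17.1 | 15.3 | 18 |
| Suicidal ideation | 14.5 | 14.5 | 13.4 | any reduction |
| Overdose | 5.9 | 5.9 | exact method needed | none |

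Seven of nine rows reproduce within 0.1 point as increases with the observed rate as one arm's rate. MDD response and PTSD response do not. For suicidal ideation, the detectable reduction from a 24.2% EUC rate is 12.0 points.

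**VR-12.** SE = SD√(4/525): 1.047 (physical, SD 12) and 1.135 (mental, SD 13). Multiplying by (2.241 + 0.842) gives 3.2 and 3.5, as printed. The reference is 2.3 (by analogy for physical). Power there is Φ(2.3/SE − 2.241) = 0.48 and 0.42.

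**Count.** As printed, 4 meet their reference (PTSD quality, MDD remission, MDD response, PTSD response) and 4 miss it (MDD quality, PTSD remission, physical and mental functioning). Four have no numeric reference: three say none and one says any reduction. On a pooled reading only MDD quality moves, giving 5 met and 3 missed.

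**The case against.** The power figures were computed after data collection, so they cannot change design or enrolment, and the confidence intervals will show which effects remain plausible. The SAP prints both hazard ratios, states the hypothesised direction clearly and tests two-sided. All of this stands, and it makes the point a correction of text.

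On the summary sentence, the SAP's wording allows either clinical meaningfulness or prior effects as the yardstick, references are given only where available, and three of the eight are by analogy. Counting only the five stated numerically, three are met and two missed. That is a fair limit: adequacy is not shown, which differs from being disproved. It still does not support a claim covering nearly all outcomes.

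Four stronger readings are tempting and should not be drawn:
- That no overdose reduction can reach 80% power. SAP 3.4.3 plans logistic regression without naming the test of the coefficient, and the likelihood-ratio test reaches 0.80 for complete elimination of a 2.1% EUC rate.
- That the claim about exploratory outcomes is contradicted. Both outcomes with a reference meet it (alcohol 0.87 v 2; overdose risk behaviours 1.7 v 25% of 12.1 = 3.0). The other three have none, so the claim is undocumented for them.
- That the shortfall against the 22-point prior effect is hidden. The SAP prints it beside the 27-point detectable difference, with a hedge.
- That the Table 9 rates are certainly pooled. The blinding statements make this likely, but the table does not say so.

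**Conclusion.** The point holds as an error in stated power. The HR of 0.45 carries the wrong direction under the SAP's own model; faster access corresponds to about 2.2, with the detectable magnitude unchanged. The 5.9-point overdose reduction is impossible under any method or either reading of the rate. The 14.5 for suicidal ideation is an increase where a reduction is sought, overstating the detectable reduction by 2.5 points (EUC rate) or 1.1 points (pooled). Table 9 shows 4 of 12 secondary outcomes meeting a reference as printed, and 5 at most.

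The recomputed figures assume equal arms, no covariate adjustment and, except for the exact overdose results, the normal approximation. The counts take by-analogy references at face value. The range of overdose power assumes that 2.1% is the EUC rate. No test, model, estimate or sample size is affected.

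**What to change.** 1. In SAP 3.5.1, state that benefit is HR above 1 and that the detectable HR is about 2.2, and give the event count used.
2. In Table 9, state whether observed rates are EUC or pooled. Restate the overdose and suicidal ideation rows as reductions, and recheck MDD response and PTSD response. If the basis is pooled, recompute the other binary rows too.
3. For overdose, name the test and use an exact calculation. With about 11 events, say that even eliminating a 2.1% EUC rate gives power from about 31% (Fisher) through 65% (z-test) to 80% (likelihood ratio), so no realistic partial reduction is detectable. Do not say categorically that no reduction reaches 80%.
4. Replace the summary sentence in SAP 3.5.2 with the numbers met and missed among outcomes that have a reference, and list the others separately. Limit the exploratory sentence to alcohol use and overdose risk behaviours. Align the secondary-outcome sentence in Protocol 9.2.

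The cost is recomputing between four and nine table rows from data the sponsor already holds, plus edits to a few sentences.
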